5.6.4. Quantitative Coronary Angiography (QCA)

Quantitative coronary angiography (QCA) images will need to be obtained at baseline (pre-procedure and post-procedure) displaying the coronary lesion in the projection demonstrating the severity of the lesion, after intracoronary administration of nitrate (recommended 100-200 µg, unless clinically contraindicated). At least two orthogonal, or near orthogonal views should be obtained.

Quantitative analysis of the coronary angiographic images will be performed by an independent core laboratory for all subjects.

5.6.5. Antithrombotic Drug Treatment

Appropriate anticoagulant therapy must be provided to the patient prior to the angioplasty procedure and must be maintained during the procedure.

5.6.6. Post-Operative Procedures

Following interventional treatment, patients will receive DAPT including a P2Y12 inhibitor in combination with aspirin for 6 months. The duration of DAPT may be changed by the prescriber at their usual clinical discretion or to account for increased bleeding risk, or co-prescription of anticoagulation.

A post-procedural 12 lead electrocardiogram (ECG), will be performed prior to hospital discharge. In addition, in the event of development of symptoms after PCI a 12-lead ECG is required to document any suspicious cardiac ischemic episode.

Cardiac troponin (cTn) (per institutional standard) will be measured in all cases at least once post procedure with one of the measurements at 18-24 hours post-procedure. If the patient is discharged prior to 18 hours post procedure, it will be measured immediately prior to discharge.

Every effort must be made to obtain cardiac enzyme values within the specified time range to help determine presence or absence of MI post-procedure. In the case of multiple measurements prior to discharge, the first enzyme measurement and the peak value should be documented on the case report forms.

If any cTn values above the reference range are noted post-procedure, per the Fourth Universal Definition, cTn measurements should continue to be performed every 6 hours for 24 hours, as per clinical practice starting from when the first elevation is noted. MI will be adjudicated according to the Fourth universal definition.

Clinical status will be assessed at discharge. All cardiac medications will be recorded.

A letter will be sent to the patient's referring physician/general practitioner, explaining his/her participation in the study and a detailed schedule of required study activities and follow up time points.

5.7. Follow-up

Follow-up assessment visits will be at the following intervals following the index procedure:

- Hospital discharge
- 30 days (\pm 1 week)
- 12 Month (\pm 1 month)
- Unscheduled visit

The following assessments and information will be collected at all follow-up visits:

- Review of concomitant medications including antithrombotic medications
- Endpoint collection
- Adverse event assessment/reporting

In addition to above assessments, for the **12-month follow-up** the following assessments will need to be performed as well:

- Physical examination
- Review of laboratory data
- 12-lead ECG

All follow-up time-points, except for 12-month time-point for which the subject needs to attend the clinic, may be completed by phone call (or if standard hospital practice during an office visit).

A summary of required follow-up procedures is listed in Table 1.

5.8. Unscheduled Visit

Investigators may see the subjects, at their professional discretion, outside of the visits described in the study protocol. If an SAE is reported during an unscheduled visit, the SAE and its treatment (CABG, re-PCI if any) should be documented in the same manner as for a study visit, per section 6.2. No additional data collection or CRFs are required at the unscheduled visit.

5.9. Subject Discontinuation

Subjects will participate in the study until they complete the 12-month post treatment assessments (per protocol). Subjects who do not complete the study per protocol may be withdrawn from the study in the following manner:

5.1.1. *Withdrawal prior and/or during index procedure*

Patients who have signed an informed consent form, but that are screen failures, will be documented as such on the subject screening log.

For patients who were declared eligible for the study but who are discontinued for any reason,

- either, prior to the commencement of PCI procedure or,
- during the procedure, as it was not possible to cross the lesion with either the guidewire or the HD IVUS catheter.

These patients will also be considered screen failures. Data until that period will be collected and the patient will be immediately exited from study. The reason for the early withdrawal must be documented in the subject screening log.

Patients that have not passed screening will not be enrolled in the study and further follow-up of these patients shall proceed according to the hospital standard procedures.

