5.3. Enrollment

After completing the informed consent, the final screening check takes place during the angiography: this will be confirmed and documented. Only once the below criteria are fulfilled can the patient be considered enrolled in the study:

All angiographic inclusion and exclusion criteria outlined in section 4.2 are fulfilled.

For the purposes of this clinical study, patients will be considered subjects after enrollment has been confirmed.

If a patient has provided informed consent but has not met one of the above criteria for enrollment inclusion into the study, he/she will be considered a screen failure.

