The CYCLOPES calcium modification algorithm illustrated in Figure 2 offers a 3-step process for the management of coronary calcification “Define, Modify, Confirm” (DMC). The algorithm is guided by intravascular ultrasound to be performed with mechanical pullback, using HD IVUS. The IVUS 1, 2, 3 Essentials Workflow should be performed at each HD IVUS acquisition throughout the algorithm[12].

CYCLOPES treatment algorithm

[figure not shown]
[figure not shown]
[figure not shown]
Pre Stent Workflow			
Adapted from IVUS 1 2 3 Essentials			
Landing zone	No disease or minimal plaque burden	Mild or moderate plaque burden $\leq 50\%$	Heavy plaque burden $\geq 50\%$ plaque burden
Measurements	 Lumen-Lumen and EEL-EEL show minimal difference	 Lumen-Lumen and EEL-EEL differ by $\geq 1\text{mm}$	 Lumen-Lumen and EEL-EEL differ substantially
Distal edge stent diameter	Size stent to L-L measurement to minimize risk of edge dissection	Size stent to L-L measurement to minimize risk of edge dissection	This is not an appropriate landing zone for a stent – seek less diseased segment
Proximal or distal postdilation balloon diameter	Size postdilation balloon to EEL but do not exceed EEL-EEL measurement	Size postdilation balloon to EEL. Downsize by 0.5mm or aim to size half way between lumen and EEL	Postdilation balloon should not be sized to EEL-EEL measurements in areas of heavy plaque burden. Balloons are likely to be oversized due to positive remodelling.

Figure 3 Pre-stent workflow based on IVUS 123 Essentials workflow

Having met the eligibility criteria outlined in section 4.2, including QCA assessment, the set-up step is initiated. This involves crossing the calcified lesion with a coronary guidewire and attempting to cross the lesion with the imaging (IVUS) catheter. If the imaging catheter does not pass through the lesion, the lesion should be predilated with an angioplasty balloon to facilitate crossing the lesion with the imaging catheter at a second attempt. For any lesions that are not crossable with an angioplasty balloon, an upfront rotational/orbital atherectomy strategy may be required to proceed.

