5.12. Additional Case Report Forms

Adverse Events (AEs)

AE forms will document a description of the AE, onset date and duration, severity, seriousness, treatment, and relatedness. The form will also document whether the event was anticipated or unanticipated.

Study Exit Form

This form will document termination of each subject's study participation and capture the reason for study exit.

NOTE: screen failures will not be captured into the eCRF.

Protocol Deviation Form

This form will document deviations from the study protocol.

6. Safety Reporting

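### Section 5.9 (5.1.1) makes eligible patients with a wired lesion screen failures when the HD IVUS catheter cannot cross. This happens after PCI has begun, conflicts with sections 5.3 and 5.12, and loses their one-year outcome.

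*Protocol*

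**What the plan says.** The rule stands in Protocol section 5.9, in the subsection numbered 5.1.1. It covers patients who had been declared eligible. One of its two triggers is discontinuation "during the procedure, as it was not possible to cross the lesion with either the guidewire or the HD IVUS catheter". The consequence is that "These patients will also be considered screen failures" and that "Data until that period will be collected and the patient will be immediately exited from study". The reason goes into the screening log, and later care follows hospital routine.

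Other sections bear on the same patients:

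- **Section 5.3** makes enrollment depend on one condition: "All angiographic inclusion and exclusion criteria outlined in section 4.2 are fulfilled". A screen failure is a consented patient who "has not met one of the above criteria for enrollment inclusion into the study, he/she will be considered a screen failure".
- **Section 4.2.1** requires that a coronary guidewire can cross the lesion. It sets no such condition for the imaging catheter. Significant calcium may be shown by angiography or by intravascular imaging.
- **Section 5.6.3** deals with a catheter that fails at first: "If the imaging catheter does not pass through the lesion, the lesion should be predilated with an angioplasty balloon", followed by a second attempt. Atherectomy is foreseen for lesions that a balloon cannot cross.
- **Appendix A** dates the start of PCI from the moment the guidewire crosses the first lesion.
- **Section 5.12** notes that "screen failures will not be captured into the eCRF".
- **Section 8.2** requires eCRF entry for the Screened set and the full analysis set (FAS), and draws the per-protocol set from the FAS. The FAS also needs a completed index procedure and assessment with the CYCLOPES algorithm.
- **The synopsis** (Design) names feasibility of the IVUS-guided algorithm, alongside efficacy, as what the trial assesses.

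**The concern.** Guidewire failure and IVUS-catheter failure get the same label but are different events. The first breaches an inclusion criterion. The second is an outcome of a procedure that has started, in a patient who may meet every criterion. Removing patients on such an outcome is exclusion after treatment start, and the lesions removed are those in which the IVUS-guided strategy could not be carried out.

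Two results are at stake. The first is feasibility: a lesion that the imaging catheter cannot cross is a direct feasibility failure, yet it leaves the denominator. The second is follow-up: patients exposed to a balloon or to atherectomy have no one-year outcome, and a later analysis plan cannot recover data that were never collected.

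**Working it through.** **Step 1. Enrollment status.** Take a consented patient whose calcium criterion is met on angiography and whose lesion the guidewire has crossed, but the IVUS catheter cannot pass.

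| Section | Status of this patient |
|---|---|
| 4.2.1 | Meets the only crossing criterion (guidewire) |
| 5.3 | Enrolled; not a screen failure as defined there |
| 5.9 (5.1.1) | Screen failure, exited at once |

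The conflict does not extend to guidewire failure. Nor does it cover a patient whose calcium eligibility depended on IVUS that was never obtained, who is properly a screen failure.

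**Step 2. Timing.** Appendix A starts PCI at wire crossing, so IVUS non-crossing in a wired lesion always follows the start of PCI. Because section 5.6.3 provides for predilatation and a new attempt, the patient may have been treated before the attempt is abandoned.

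**Step 3. Data.** Section 5.1.1 says data to that point are collected. Section 5.12 bars screen failures from the eCRF, and section 11.1 places all required data in the eCRF. A generous reading puts these patients in the Screened set of section 8.2, but its extra subjects are followed only to discharge. Once 5.1.1 is applied, no reading yields one-year follow-up.

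**Step 4. Size.** The protocol gives no non-crossing rate, expected TLF or expected strategy success, so there is no figure to reproduce. All rates below are assumptions. Let f be the share of started procedures lost to IVUS non-crossing, with 500 patients retained.

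- Patients removed = 500 × f/(1 − f)
- Strategy success over all attempted = 0.80 × (1 − f), with assumed success of 80% in those retained and non-crossers counted as failures
- TLF over all attempted = 0.10 × (1 − f) + q × f, with assumed TLF of 10% in those retained and q = 20% to 30% in those removed

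| f | Removed | Strategy success | TLF | Non-crossing rate (exact 95% CI) |
|---|---|---|---|---|
| 1% | 5 | 79.2% | 10.1–10.2% | 5/505 = 1.0% (0.3–2.3) |
| 2% | 10 | 78.4% | 10.2–10.4% | 10/510 = 2.0% (0.9–3.6) |
| 5% | 26 | 76.0% | 10.5–11.0% | 26/526 = 4.9% (3.3–7.2) |

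**Step 5. Comparison with sampling error.** Exact 95% intervals are 76.2–83.4% for 400/500 and 7.5–13.0% for 50/500.

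- Strategy success reaches its lower limit at f = 1 − 0.7622/0.80 = 4.7%, about 25 patients.
- With TLF in every removed patient, the upper limit is reached at f = (0.1297 − 0.10)/0.90 = 3.3%, about 17 patients.
- At f = 5%, TLF in the removed patients would have to exceed (0.1297 − 0.095)/0.05 = 69%.

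**The case against.** The strongest reply is that the plan is about imaged patients and shows it. The FAS is limited to subjects assessed with the algorithm, baseline IVUS is described for all patients, and 5.1.1 states the exclusion. The aim in section 1.3 is to validate an imaging-based algorithm, no endpoint is named feasibility, and the analysis is descriptive with no hypothesis. This largely stands. A reader might infer that the primary TLF estimate is biased, or that the restriction to imaged patients is hidden. The documents support neither: for the population the FAS describes, the rule does not distort TLF.

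The word also in 5.1.1 can be read as a deliberate extension of the screen-failure definition in 5.3. That explains the intent, but it leaves one patient with two statuses.

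A reader might also take section 5.6.3 ("Having met the eligibility criteria outlined in section 4.2, including QCA assessment, the set-up step is initiated") as proof that eligibility is settled before any crossing attempt. It cannot carry that weight, because the same text places guidewire crossing inside set-up although guidewire crossing is itself an inclusion criterion. The conflict rests on sections 4.2.1 and 5.3 and Appendix A.

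Finally, section 6.2 starts procedural SAE documentation after calcium modification. One might infer that 5.1.1 leaves set-up complications uncovered. That start point applies to every subject and is separate from 5.1.1. Whether a set-up balloon or atherectomy counts as calcium modification is unclear rather than plainly excluded: section 7.1 lists non-compliant balloons among the calcium modification devices, while section 2 lists them as standard devices. Section 6.2 also has the investigator report all AEs and refers to a safety plan that is not at hand.

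**Conclusion.** The point holds for angiographically eligible patients with a wired lesion and IVUS non-crossing. Their status is contradictory between sections 5.3 and 5.9, their data capture is contradictory between sections 5.9 and 5.12, and their one-year outcome is lost after PCI has begun.

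The numerical effect is probably small. On the assumed rates, TLF over all attempted procedures is 0.1 to 0.4 points higher at 1–2% non-crossing and up to 1.0 point higher at 5%. Strategy success is 0.8 to 1.6 points lower at 1–2% and 4.0 points lower at 5%. These figures scale with a non-crossing rate that the protocol does not give. The main loss is that feasibility, as named in the synopsis, cannot be answered from the analysis data; only a count and reason survive in the screening log. It should be fixed while outcomes can still be collected.

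**What to change.** In section 5.9 (5.1.1), split the rule:

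1. Guidewire failure, exit before PCI starts, and IVUS-dependent eligibility that was never confirmed remain screen failures.
2. Patients eligible by angiography, with a wired lesion that the IVUS catheter cannot cross, stay enrolled. Enter them in the eCRF, record their procedural SAEs and follow them for TLF to 12 months.

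Reconcile sections 5.3, 5.12 and 8.2 with this, and clarify in section 6.2 that procedural SAEs in these patients are documented. Say whether they count towards the 500.

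Keep the FAS as the algorithm-assessed population for the primary analysis and state this as its target. As supplementary results, report the IVUS non-crossing rate with its exact confidence interval, strategy success over all attempted procedures with non-crossers as failures, and TLF over all attempted procedures. Moving these patients into the primary FAS is not needed and would change what it estimates, since their later care may lie outside the algorithm.

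The cost is text edits and the existing follow-up visits for a few more patients: about 5 to 10 at 1–2% non-crossing, about 26 at 5%. The supplementary success rate will be slightly lower than the primary one.

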5.1.2. Patient withdrawal

Subjects may withdraw their consent and discontinue participation in the study at any time for any reason or no reason, without jeopardizing their medical care. If a subject withdraws consent it will be documented on the study exit form, and the reason for withdrawal will be requested.

All data obtained until the date of withdrawal will be kept and entered into the efficacy and safety analysis. If the patient explicitly requests complete deletion of the records, they will be made aware that data pertaining to serious adverse events (SAEs) will be retained. This should be documented by the site. Subjects will not be replaced.

Once the subject is withdrawn, further follow-up of the patients shall proceed according to the hospital standard procedures.

5.1.3. Investigator Withdrawal

Subjects may be withdrawn by the investigator prior to receiving a study treatment for the following reason:

If, on the day of procedure, it is determined by the investigator that the subject is no longer an appropriate candidate for the index procedure then the patient will be withdrawn from the study and will not receive the treatment.

The investigator may decide to withdraw the subject from the study at any time based on medical judgment. In all instances of withdrawal, data collected up to the time of subject withdrawal may be used in the study. Subjects withdrawn from the study after being treated based on the study algorithm or procedures will not be replaced. The site should complete a study exit form.

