5.10. Premature Termination or Suspension of the Study

The Sponsor may decide to suspend or prematurely terminate the clinical study in one or more investigation sites if e.g. information that the risk to the study subjects is higher than initially indicated becomes available.

In the case of an early termination of the study, the regulatory authority(ies) and ethic committee(s) (ECs) should be informed according to local and national regulations. The reasons for termination should be provided and documented. An appropriate schedule for termination will be instituted.

For patient safety reasons, patients already enrolled in the study will continue to be followed for the planned course of study described in this protocol.

Patients will be informed that the study has been prematurely terminated and about the reason for this termination.

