8.3.3. Primary analysis

The study will have co-primary endpoints. The co-primary endpoints are minimum stent area (MSA) at the site of maximum calcification measured at the end of the index procedure and target lesion failure (TLF) defined as the composite of cardiac death, non-fatal myocardial infarction related to the target vessel, and unplanned ischemia-driven target lesion revascularization at one-year post-procedure. MSA is a numerical measurement in millimeters, measured at the independent imaging core laboratory. TLF is a binary endpoint (TLF or no TLF).

The primary analysis will be conducted on the FAS and will estimate the proportion of TLF at 1-year with corresponding exact two-sided 95% CI. Descriptive analyses for MSA will be performed.

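### Section 5.1.3 lets an investigator exit an already treated patient on medical judgment, and the protocol makes no provision to collect 1-year TLF or vital status afterwards

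*Protocol*

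**What the plan says.** Section 5.1.3 (Investigator Withdrawal) begins with patients found unsuitable before treatment. It then adds a right with no time limit: "The investigator may decide to withdraw the subject from the study at any time based on medical judgment". That this reaches treated patients is explicit in the same paragraph: "Subjects withdrawn from the study after being treated based on the study algorithm or procedures will not be replaced". On data it says: "In all instances of withdrawal, data collected up to the time of subject withdrawal may be used in the study". It also asks the site to complete a study exit form, which section 5.12 describes as follows: "This form will document termination of each subject's study participation and capture the reason for study exit".

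Section 5.1.2, on patients who withdraw consent, states: "Once the subject is withdrawn, further follow-up of the patients shall proceed according to the hospital standard procedures". Section 5.1.3 has no sentence of its own on follow-up after an investigator's withdrawal.

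On the analysis, section 8.3.3 states: "The primary analysis will be conducted on the FAS and will estimate the proportion of TLF at 1-year with corresponding exact two-sided 95% CI". Section 8.2 describes FAS subjects as followed to the end of study at 12 months. Section 8.3.1 sets the general denominator for percentages as the non-missing values, unless otherwise specified.

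Two neighbouring sections lean towards retention. Section 5.1.4 keeps a subject who cannot be reached in the study until the 1-year contact. Section 5.10, on early termination of the study, says: "For patient safety reasons, patients already enrolled in the study will continue to be followed for the planned course of study".

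**The concern.** The clause removes the patient from the study, not merely from a procedure. For most patients calcium modification and stenting are complete at the index procedure, and what remains is the observation that supplies the TLF endpoint. An investigator's medical decision about a treated patient need not end that observation, but as written it can.

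Two features make this more than untidy wording. First, a medical reason for exit is plausibly related to the risk of cardiovascular death, target-vessel infarction or target lesion revascularization, so the missing outcomes would not be a random sample. Second, the study has one arm and reports a single proportion, so no comparator exists in which a similar loss could offset the error. The analysis plan can choose how to treat missing outcomes, but it cannot recover events that were never collected. Retention has to be settled in the protocol.

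**Working it through.** **Step 1: does follow-up end?** No single sentence says so for an investigator's withdrawal. It follows from three provisions read together:

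- 5.1.3 provides only for data up to the withdrawal.
- 5.1.3 requires the exit form, and 5.12 makes that form the record that participation has ended.
- No section provides for endpoint or vital-status collection after such an exit.

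The sentence in 5.1.2 about hospital-standard follow-up is consistent with this, but it is written for withdrawal of consent and is only supporting evidence.

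**Step 2: what happens to the TLF proportion?** If 8.2 is read as a condition, a patient not followed to 12 months is outside the FAS. If it is read as a description, a patient with no 1-year TLF status is still left out of the denominator by the general rule in 8.3.1. Either way the patient can leave the proportion. On the strict reading of 8.2, even a TLF recorded before exit could go uncounted. That sits badly with 5.1.2, which enters data up to withdrawal into the analysis, while 5.1.3 says only that such data may be used.

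**Step 3: size.** The protocol gives N = 500 (section 8.4) but no expected TLF rate, precision target or withdrawal rate, so there is no figure of its own to reproduce. All rates below are assumptions.

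Let *w* be the share exited after treatment, *r* their TLF risk (events unseen) and 8% the risk in those who remain. With exited patients outside the denominator, the reported rate is 8.0% and the true rate is

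true TLF = 0.08 × (1 − *w*) + *r* × *w*

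| *w* | *r* | True TLF | Understatement |
|---|---|---|---|
| 2% (10 patients) | 20% | 0.0784 + 0.0040 = 8.24% | 0.24 points |
| 2% (10 patients) | 30% | 0.0784 + 0.0060 = 8.44% | 0.44 points |
| 5% (25 patients) | 20% | 0.0760 + 0.0100 = 8.60% | 0.60 points |
| 5% (25 patients) | 30% | 0.0760 + 0.0150 = 9.10% | 1.10 points |

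For scale, the exact (Clopper-Pearson) 95% interval for 40/500 is 5.78% to 10.73%, a half-width of (10.73 − 5.78)/2 = 2.48 points.

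**Step 4: a wider range.** Now fix the true overall rate at 10% (50 events in 500) and let exited patients have *k* times that risk, all unseen:

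observed = (50 − *W* × 0.10 × *k*) / (500 − *W*)

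- *W* = 25, *k* = 1: (50 − 2.5)/475 = 10.0%. There is no bias if the exits are unrelated to risk.
- *W* = 25, *k* = 2: (50 − 5)/475 = 9.5%.
- *W* = 25, *k* = 3: (50 − 7.5)/475 = 8.9%.
- *W* = 50, *k* = 3: (50 − 15)/450 = 7.8%, exact interval 5.5-10.7%, against 7.5-13.0% with all 500 followed.

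For true rates of 5%, 10% or 15% and risks up to threefold, exiting 1-2% of patients shifts the estimate by at most about 0.6 points.

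**The case against.** Several points on the other side stand.

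- **Treatment is not always finished on day 0.** Section 5.6.2 allows the operator to defer stenting to a staged procedure with a further IVUS recording. For those patients a study procedure lies ahead, and an investigator may have reason to stop it. A reader might infer that withdrawal after the index procedure can never serve a purpose. The protocol does not support that.
- **Remaining contact is not always just a phone call.** The synopsis allows a phone visit at 12 months, but section 5.7 requires clinic attendance with examination, laboratory review and ECG.
- **Section 5.10 is not a contradiction.** It governs termination of the study by the sponsor and speaks of enrolled patients. It shows that the protocol values continued follow-up, but it does not conflict with 5.1.3.
- **Many events would precede the exit.** A complication or repeat intervention that prompts withdrawal may itself be a TLF component or an SAE, already recorded. Only patients exited while still event-free create the understatement, provided earlier events are counted. The protocol names no medical grounds for exit after treatment, so the link to risk is plausible but not documented.
- **The size is small and assumed.** No withdrawal frequency is given, the main illustration stays inside the interval's half-width, and the study tests no hypothesis, so no decision threshold is crossed.
- **The denominator rules reach further.** They also affect consent withdrawals and losses to follow-up, which a change to 5.1.3 does not address.

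None of this answers the core point. The discretion is open-ended, it expressly covers treated patients, and nothing collects their outcomes afterwards.

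**Conclusion.** The point holds as a correctable weakness in the withdrawal rule. Section 5.1.3 permits loss of co-primary endpoint data in treated, consenting and reachable patients, for reasons that are plausibly informative, and the likely direction is a lower observed 1-year TLF. That follow-up ends is an inference from 5.1.3 and 5.12, not a quoted rule.

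Under the assumptions of 2-5% exited, a TLF risk of 20-30% in them and 8% in the rest, the understatement is about 0.2-1.1 percentage points. That is below the half-width of about 2.5 points. It would be near zero if the right is hardly used or the exits are unrelated to risk. It would be larger if use were frequent: about 2.2 points (10.0% against 7.8%) with 10% exited at threefold risk. The documents do not show which case applies, and they do not show that the TLF estimate will be materially wrong. The case for changing the text is that the loss is avoidable at little cost.

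**What to change.** Add to 5.1.3 that, for enrolled subjects who have had the index procedure and are not screen failures under 5.1.1, an investigator's medical judgment may change care or stop any remaining study procedure but does not end study follow-up. TLF, SAEs and vital status continue to be collected to 12 months, by phone or from records, unless the subject withdraws consent. State also that a TLF recorded before any exit counts in the TLF analysis, and align the FAS wording in 8.2 with that.

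The exclusion of 5.1.1 screen failures is needed. Section 5.6.3 allows up-front atherectomy before the IVUS catheter has passed, and 5.1.1 then exits immediately a patient whose lesion the catheter cannot cross. A trigger based on the start of calcium modification would put the two sections in conflict.

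The cost is a few sentences, matching instructions for the exit form, and one or two extra contacts or record checks for a few patients. Decisions on clinical care stay with the investigator.
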